### **Product Quality Complaint (PQC)**

A product quality complaint is related to a potential quality issue during manufacturing, packaging, release testing, stability monitoring, dose preparation, storage or distribution of the product, or delivery system. Not all PQCs involve a subject. Lot and batch numbers are of high significance and need to be collected whenever available.

Examples of PQC include but not limited to:

- Functional Problem: e.g., altered delivery rate in a controlled release product
- Physical Defect: e.g. abnormal odor, broken or crushed tablets/capsules
- Potential Dosing Device Malfunction: e.g., autoinjector button not working, needle detaching from syringe
- Suspected Contamination
- Suspected Counterfeit.

### **Serious Adverse Event (SAE)**

A serious adverse event based on ICH and EU Guidelines on Pharmacovigilance for Medicinal Products for Human Use is any untoward medical occurrence that at any dose:

- Results in death
- Is life-threatening
- (The subject was at risk of death at the time of the event. It does not refer to an event that hypothetically might have caused death if it were more severe.)
- Requires inpatient hospitalization or prolongation of existing hospitalization
- Results in persistent or significant disability/incapacity
- Is a congenital anomaly/birth defect
- Is a suspected transmission of any infectious agent via a medicinal product
- Is medically important\*

\*Medical and scientific judgment should be exercised in deciding whether expedited reporting is also appropriate in other situations, such as important medical events that may not be immediately life threatening or result in death or hospitalization but may jeopardize the subject or may require intervention to prevent one of the other outcomes listed in the definition above. These should usually be considered serious.

**NOTE: Death for ANY reason should be reported as a SERIOUS ADVERSE EVENT.**

For reports of hospitalization, it is the sign, symptom or diagnosis which led to the hospitalization that is the serious event for which details must be provided.

Any event requiring in-patient hospital admission (or the prolongation of hospitalization) must be reported as an SAE. Events that do not meet the criteria for SAE reporting are:

- Reasons described in the Protocol, e.g. drug administration, Protocol-required testing
- Social reasons, e.g. overnight stay because of distance between home and hospital
- Surgery or procedure planned and documented prior to entry into the Study.

Any event requiring hospitalization or prolongation of hospitalization that occurs during the study must be reported as a serious adverse event, except hospitalizations for the following:

- Hospitalizations not intended to treat an acute illness or adverse event (e.g., social reasons such as pending placement in long-term care facility)
- Surgery or procedure planned before entry into the study. [Note: Hospitalizations that were planned before the start of data collection and where the underlying condition for which the hospitalization was planned has not worsened will not be considered serious adverse events. Any adverse event that results in a prolongation of the originally planned hospitalization is to be reported as a new serious adverse event.]

The cause of death of a subject in a study within 30 days of the last dose of study drug, whether or not the event is expected or associated with the study drug, is considered a serious adverse event.

### **Unlisted (Unexpected) Adverse Event/Reference Safety Information**

An adverse event is considered unlisted if the nature or severity is not consistent with the applicable product reference safety information. For a medicinal product(s) with a marketing authorization, the expectedness of an adverse event will be determined by whether or not it is listed in the applicable product information.

### **III. Special Situations**

Safety events of interest for a Janssen medicinal product that require expediting reporting and/or safety evaluation include, but are not limited to:

- Drug exposure during pregnancy (maternal and paternal)
- Overdose of a Janssen medicinal product
- Exposure to a Janssen medicinal product from breastfeeding
- Suspected abuse/misuse of a Janssen medicinal product
- Inadvertent or accidental exposure to a Janssen medicinal product
- Any failure of expected pharmacological action (i.e., lack of effect) of a Janssen medicinal product
- Medication error involving a Janssen medicinal product (with or without patient exposure to the Janssen medicinal product, e.g., name confusion)
- Suspected transmission of any infectious agent via a medicinal
- Unexpected therapeutic or clinical benefit from use of a Janssen medicinal product

These safety events may not meet the definition of an adverse event; however, they are treated in the same manner as adverse events. Special situations should be recorded on the Adverse Event page of the CRF.

Any special situation that meets the criteria of a serious adverse event should be recorded on a Serious Adverse Event Report Form and be reported to Janssen Scientific Affairs **within 24 hours of becoming aware of the event.**

### **IV. Pregnancy**

All initial reports of pregnancy must be reported to Janssen Scientific Affairs by the Sponsor Investigator **within 24 hours of their awareness of the event** using the Serious Adverse Event Form. Abnormal pregnancy outcomes (e.g. spontaneous abortion, stillbirth, and congenital anomaly) are considered serious adverse events and must be reported using the Serious Adverse Event Form.

Any subject who becomes pregnant during the study must be promptly withdrawn from the study and discontinue further study treatment.

Because the effect of the Janssen medicinal product on sperm is unknown, pregnancies in partners of male subjects exposed to a Janssen medicinal product will be reported by the Sponsor Investigator **within 24 hours of their awareness of the event** using the Serious Adverse Event Form. Depending on local legislation this may require prior consent of the partner.

Follow-up information regarding the outcome of the pregnancy and any postnatal sequelae in the infant will be required.

## **V. Reporting Procedures for Adverse Events and Pregnancies [and/or Pregnancies in Partners]**

All adverse events, whether serious or non-serious, related or not related, special situations, pregnancy exposures and/or pregnancies in partners following exposure to a Janssen medicinal product are to be documented by the investigator and recorded in the CRF and in the subject's source records. Investigators must record in the CRF their opinion concerning the relationship of the adverse event to a Janssen medicinal product.

All (serious and non-serious) adverse events reported for a Janssen medicinal product should be followed-up in accordance with clinical practice.

All serious adverse events that have not resolved by the end of the study, or that have not resolved upon discontinuation of the subject's participation in the study, must be followed until any of the following occurs:

- The event resolves
- The event stabilizes
- The event returns to baseline, if a baseline value/status is available
- The event can be attributed to agents other than the study drug or to factors unrelated to study conduct
- It becomes unlikely that any additional information can be obtained (subject or health care practitioner refusal to provide additional information, lost to follow-up after demonstration of due diligence with follow-up efforts)

All serious adverse events, pregnancy exposures and/or pregnancies in partners for Janssen medicinal products under study should be reported directly by the Sponsor Investigator, **within 24 hours of becoming aware**, to Janssen Scientific Affairs using the Janssen Scientific Affairs Serious Adverse Event Report Form. In the event the study is blinded, the Sponsor Investigator will submit an unblinded SAE or pregnancy exposure report to Janssen Scientific Affairs.

All follow-up information for serious adverse events that are not resolved at the end of the study or by the time of patient withdrawal must be reported directly by the Sponsor Investigator, **within 24 hours becoming aware**, to Janssen Scientific Affairs using the Janssen Scientific Affairs Serious Adverse Event Report Form.

## **VI. Product Quality Complaints for Janssen Medicinal Products**

A PQC may have an impact on the safety and efficacy of the product. Timely, accurate, and complete reporting and analysis of PQC information from studies are crucial for the protection of patients, investigators, and Janssen Scientific Affairs, and are mandated by regulatory agencies worldwide. Janssen Scientific Affairs has established procedures in conformity with regulatory requirements worldwide to ensure appropriate reporting of PQC information. Lot and/or Batch #s shall be collected or any reports of failure of expected pharmacological action (i.e., lack of effect).

All initial PQCs involving a Janssen product under study must be reported to Janssen Scientific Affairs by the Sponsor Investigator **within 24 hours after being made aware of the event**.

If the defect for a Janssen product under study is combined with either a serious adverse event or non-serious adverse event, the Sponsor Investigator must report the PQC to Janssen Scientific Affairs according to the serious adverse event reporting timelines. A sample of the suspected product should be maintained for further investigation if requested by Janssen Scientific Affairs.

#### **VII. Maintenance of Safety Information**

All safety data should be maintained in a clinical database in a retrievable format. The Institution and Sponsor Investigator shall provide all adverse events, both serious and non-serious, in report format. However, in certain circumstances more frequent provision of safety data may be necessary, e.g. to fulfill a regulatory request, and as such the data shall be made available within a reasonable timeframe at Janssen Scientific Affairs's request.

#### **VIII. Transmission Methods:**

The following methods are acceptable for transmission of safety information to Janssen Scientific Affairs:

- Electronically via Janssen SECURE Email service (preferred)
- For business continuity purposes, if SECURE Email is non-functional:
  - Facsimile (fax), receipt of which is evidenced in a successful fax transmission report
- Telephone (if fax is non-functional).

Please use the contact information and process information provided by Janssen Scientific Affairs.

#### **IX. Procedures for Reporting Adverse Events (AE), Serious Adverse Events (SAE), Pregnancy, and Product Quality Complaints (PQC) to Janssen Scientific Affairs**

##### **A. AEs, SAEs, Special Situations and Pregnancy Reporting.**

The Institution and the Sponsor Investigator will transmit SAEs and Special Situations in a form provided by Janssen Scientific Affairs in accordance with Section VIII Transmission methods, in English **within 24-hours** of becoming aware of the event(s).

All available clinical information relevant to the evaluation of a related SAE or Special Situation is required.

- The Institution and/or Sponsor Investigator are responsible for ensuring that these cases are complete and if not are promptly followed-up. A safety report is not considered complete until all clinical details needed to interpret the case are received. Reporting of follow-up information should follow the same timeline as initial reports.
- Copies of any and all relevant correspondences with regulatory authorities and ethics committees regarding any and all serious adverse events, irrespective of association with the Janssen Product under study, are to be provided to Janssen Scientific Affairs using a transmission method in Section VIII **within 24 hours of such report or correspondence being sent to applicable health authorities.**

##### **B. PQC Reporting**

The Institution and the Sponsor Investigator will report any suspected PQC to the Janssen contact within 24 hours of becoming aware of the complaint. The product should be quarantined immediately and if possible, take a picture.

**X. Reconciliation of SAEs**

At a minimum, on a quarterly basis and at the end of the Study, Janssen Scientific Affairs will provide to the Institution and/or Sponsor Investigator, a listing of all SAEs reported to Janssen Scientific Affairs. The Sponsor Investigator will review this listing and provide any discrepancies to Janssen Scientific Affairs.

Upon request, Institution and/or Sponsor Investigator shall provide Janssen Scientific Affairs with a summary list of all SAEs, and AEs of Special Interest and Special Reporting Situation reports to date, for reconciliation purposes.

**XI. Dissemination of Safety Information from Janssen Scientific Affairs to Institution/Sponsor Investigator**

Janssen Scientific Affairs agrees to provide to the Sponsor Investigator SUSAR reports for the Study Product as they become available until all subjects in the Protocol have completed their last Study visit according to the Protocol (i.e. Last Subject Last Visit has occurred).

## 6 STUDY SCHEMATIC: TIME AND EVENTS SCHEDULE

Procedure	Phone Screening (Before week -2)	Screening Visit (Week -2)	Baseline/Randomization Visit 1 (Week 0)	During Treatment Visit 2 (Week 8)	End-of-Treatment Visit 3 (Week 16)	Follow up phone call (Week 20)
Eligibility Assessments						
Informed Consent		X				
Inclusion / Exclusion Criteria	X	X				
Medical History		X				
Safety Assessments						
Physical Examination		X			X	
Targeted Physical Examination (as needed)			X	X	X	
Vital Signs		X	X	X	X	
Assessment of Signs and Symptoms		X	X	X	X	
Adverse Events Assessment			X	X	X	X
Laboratory Tests (Biochemical)		Screening	X	X	X	
Urine Pregnancy Test (As needed)		X	X	X	X	
Spot Urine Sample			X	X	X	
Waist/Hip Measurements			X	X	X	
Body Composition Scale			X	X	X	
Efficacy Assessments						
Peripheral blood draw for CD34+cell harvest			X	X	X	
Pulse wave analysis and Pulse wave velocity assessment			X	X	X	
RMR			X	X	X	
Clinical Drug Supplies						
Randomize			X			
Dispense Study Treatment			X	X		

### **RESEARCH STUDY DESIGN AND METHODS**

#### **Patient Definition and Selection:**

Adults aged 30-70 years will be recruited mainly from the GWU MFA research patient database provided by MFA Information Technology, and then contacted via email and phone, from the endocrinology and other provider clinics at GWU and through referrals from the Veterans Affairs (VA) clinics. Suitable advertisements for the study patient enrollment will be posted. Patients will be included in the study if they have been diagnosed with type 2 diabetes within the previous 15 years using criteria of the American Diabetes Association, and are currently treated with any combination of the following anti-diabetic therapies: metformin (1-2 grams), insulin, GLP-1 agonists, a DPP-IV inhibitor, or sulfonylureas. We wanted to capture a population where the subjects will be classified as having early stage of diabetes where endothelial dysfunction can be reversed. Late stages of diabetes may be associated with irreversible vascular damage. We plan to enroll subjects with HbA1C between 7.0% and 10% (both inclusive) and with BMI 25-39.9 kg/m^2 (both inclusive). Post enrollment, patients will be randomized to Cana 100 mg or placebo as detailed in Study Design for direct comparison between the two regimens.

Before any study procedures are performed, subjects will have the details of the study described to them, and they will be given a written informed consent document to read. Then, if subjects consent to participate in the study, they will indicate that consent by signing and dating the informed consent document in the presence of study personnel.

### **Recruitment:**

Subjects will be recruited from the physician clinics at GWU, Medical Faculty Associates, where [name] is a clinician, as well as through referral from the VA. All patients will receive counseling regarding the study aims and methods.

### **Study Design Overview:**

We propose a 2-arm randomized, double-masked, placebo-controlled, parallel group, longitudinal study of 16-weeks duration. (See study design below), recruited over 2 years. The 16 week time interval has been previously shown adequate to observe changes in endothelial progenitor stem cells, biochemistry and importantly, PWV changes. Patients will be randomized to 2 groups:

Control, (n=20), metformin, insulin or Combo + Placebo

Treatment, (n=20) metformin, insulin or Combo + Cana 100mg

This proposed study is based on patients with type 2 diabetes, who are on any combination of the following anti-diabetic therapies: metformin (1-2 grams), insulin, GLP-1 agonists, a DPP-IV inhibitor, or sulfonylureas but still remain poorly controlled with HbA1C between 7.0% and 10% (both inclusive), but not overtly out of control (> 10% of HbA1C).

Though our study is over 16 weeks we do not anticipate significant drop in HbA1C in between the two groups in this relatively short time period to act as a confounding factor on CD34+ cell number, function and gene expression.

Subjects will be taking 100 mg of Cana or placebo. Dose titration of metformin, will not be allowed. Dose titration of insulin will be allowed to avoid hypoglycemia while maintaining HbA1C under 10%.

Most clinical studies looking at HbA1C reduction were of a much longer duration of 6 months or above and most DPP-4 inhibitor studies are with animal EPCs where comparison with human CD34+ population is difficult to make. In one study where saxagliptin was used for 12 weeks

in drug-naïve type 2 diabetes patients there was placebo-subtracted HbA1c reduction noted of 0.45-0.63%. It showed mean placebo-subtracted reductions in fasting serum glucose of 20 mg/dL. From our laboratory studies of in vitro human EPC studies we do not think glucose level change of 20 mg/dL is significant enough to account for changes in EPC number, function and gene expression. However we will take the possibility of glycemia change/ reduction in experimental arm into account during statistical analysis of the results between the Canagliflozin and placebo groups.

*Visits with outcome measurements* will be scheduled for the morning while overnight fasting (except water) to reduce diurnal variability, and clinical parameters will be obtained at scheduled office visits as depicted in the study schema and will be measured at each outcome visit as follows:

**Week -2:** Subjects will be phone screened to determine initial eligibility. If the phone-screening indicates possible eligibility, then the subjects will come to an in-person screening visit that same week (If within two weeks that is acceptable).

In-person screening (Week -2): Subjects will be screened and eligibility will be verified based on physical and laboratory tests. Equal numbers of male and female patients will be recruited.

**Week 0:** At this stage patients will be randomized into the study. Subjects will have the first set of measurements. We will make sure that patients still meet the inclusion criteria. They will be started on medication or placebo.

**Weeks 0, 8 and 16:** Subjects will all have the same measurements and will continue on study medication or placebo. All primary and secondary measures as outlined before will be carried out.

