**Sponsor: The George Washington University Medical Faculty Associates**

**Funding Source: Janssen Scientific Affairs, LLC**

## PROTOCOL SYNOPSIS

Protocol Title:	Role of Canagliflozin on gene expression and function of CD34+ endothelial progenitor cells in patients with type 2 diabetes
Site Numbers & Names	GWU Medical Faculty Associates
Research Hypothesis:	Type 2 diabetes is associated with poor stem cell number and function. Poor viability and function of EPCs in diabetes affects the repair and regeneration of the endothelium. We hypothesize that use of Canagliflozin (Cana), along with certain anti-diabetic drugs may help reduce cardiovascular risk by improving EPC survival and function above and beyond adequate glucose metabolism control.
Study Schema: Drugs / Doses / Length of Treatment	
We propose a 2-arm randomized, parallel group, longitudinal study of 16-week intervention duration. The 16-week time interval has been previously shown adequate to observe changes in biochemistry, EPCs and, importantly, pulse wave velocity (PWV) changes. Patients will be randomized to 2 groups:
 
Control (n=20) Concomitant Anti-Diabetic Therapy + Placebo.  Treatment (n=20) Concomitant Anti-Diabetic Therapy + Cana 100mg.

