
# 1 RESEARCH HYPOTHESIS

We hypothesize that Cana may be able to improve number and function of CD34+ endothelial progenitor cells. We also propose that this expected cardiovascular benefit is independent of HbA1C reduction.

In this proposed study we plan to recruit patients with type 2 diabetes, who are on any combination of the following anti-diabetic therapies: metformin (1-2 grams), insulin, GLP-1 agonists, a DPP-IV inhibitor, or sulfonylureas, but still remain inadequately controlled with HbA1C between 7.0% and 10% (both values inclusive), but not overtly out of control (> 10% of HbA1C).

Subjects will begin taking 100 mg of Cana or placebo after initial 4 weeks. Subjects will be withdrawn from the study if the medication or placebo is not tolerated.

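### The hypothesis of a CD34+ benefit independent of HbA1c cannot be established by this two-arm placebo design, which estimates only the total effect of adding canagliflozin

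*Combined protocol and SAP*

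**What the plan says.** Two places state the hypothesis. The synopsis expects canagliflozin to reduce cardiovascular risk by "improving EPC survival and function above and beyond adequate glucose metabolism control". Section 1 (Research Hypothesis) adds: "We also propose that this expected cardiovascular benefit is independent of HbA1C reduction".

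Section 6, Study Design Overview, gives three reasons for discounting glycaemia as an explanation:

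- **Duration.** "we do not anticipate significant drop in HbA1C in between the two groups in this relatively short time period". The sentence goes on to limit this to a drop that would confound CD34+ number, function and gene expression.
- **Size of the glucose change.** It cites a study "where saxagliptin was used for 12 weeks" in drug-naive patients, where "there was placebo-subtracted HbA1c reduction noted of 0.45-0.63" (in HbA1c %). "It showed mean placebo-subtracted reductions in fasting serum glucose of 20 mg/dL". From the group's laboratory work, "we do not think glucose level change of 20 mg/dL is significant enough to account for changes in EPC number, function and gene expression".
- **Analysis.** It undertakes to allow for glycaemic change when the arms are compared.

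Section 7, Data Analysis, carries out the third point with glucose as a time-varying nuisance covariate. It warns against a causal reading and says that any relation found is association only. HbA1c is not named as a covariate.

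The primary objective in sections 2 and 6 is worded differently from the hypothesis. It asks whether four months of canagliflozin changes CD34+ number, gene expression and function or migration, and does not mention independence.

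**The concern.** A glucose-lowering drug is added in one arm only, in patients enrolled at HbA1c 7.0-10.0%. If CD34+ outcomes improve, the improvement may run through lower glucose, through a direct action on the cells, or both. The Introduction raises exactly this question for the drug class, so readers will look to the trial for an answer.

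The hypothesis claims the second route. The main reason offered for setting the first aside is that 16 weeks is short, yet the only HbA1c figure the protocol supplies comes from a 12-week study and shows the arms separating. If the wording stands, a positive CD34+ result could be reported as a direct, HbA1c-independent effect that the data cannot support.

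**Working it through.** **1. What the design identifies.** Randomisation compares canagliflozin with placebo, both on background therapy. That contrast is the total effect. To isolate a part not mediated by glycaemia, the trial would need a comparator with similar glucose lowering, or a mediation analysis with stated assumptions. Neither is planned. Section 6 also allows insulin titration during treatment, so background glucose lowering can differ by arm.

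**2. The duration rationale against the protocol's own figure.** The cited study ran 12 weeks and this trial runs 16. The cited placebo-subtracted fall is 0.45-0.63%. The figure comes with no SD or sample size, so it cannot be re-derived. It concerns saxagliptin in drug-naive patients, and the documents give no HbA1c figure for canagliflozin. It shows that a gap can open in less time than this trial allows. It does not show what gap canagliflozin will produce here.

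**3. The in vitro argument.** The supporting data are not in the documents. The Introduction says that hyperglycaemia is toxic to CD34+ cells and reports SGLT2 expression at 20 mM glucose. A change of 20 mg/dL is about 1.1 mM, so these statements neither confirm nor refute the judgement that such a change is too small.

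**4. How well the trial can measure an HbA1c gap (illustration).** Inputs: 20 per arm with 20% dropout (Introduction), so 20 × (1 − 0.20) = 16 per arm, which matches the plan's figure; alpha 0.05 (synopsis), taken as two-sided; gap 0.45-0.63 points; SD of HbA1c change not in the documents, assumed 0.6-1.2 points.

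- SE = SD × √(2/16)
- 95% CI half-width = t(0.975, 30 df) × SE = 2.042 × SE
- Power from the noncentral t distribution, 30 df, noncentrality = gap/SE

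| Assumed SD | SE | Half-width | Power, gap 0.45 | Power, gap 0.63 |
|---|---|---|---|---|
| 0.6 | 0.212 | 0.43 | 54% | 82% |
| 0.8 | 0.283 | 0.58 | 34% | 58% |
| 1.0 | 0.354 | 0.72 | 23% | 41% |
| 1.2 | 0.424 | 0.87 | 18% | 30% |

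With an observed difference of exactly zero, the interval would still include 0.45 at SD 0.8 (0.58 > 0.45), and would include 0.63 as well at SD 1.0 (0.72 > 0.63). With all 20 per arm retained, the half-width is 0.38-0.77 and power runs from 21% to 90%.

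**5. Whether glucose adjustment isolates a direct effect (illustration).** Assume no direct effect at all, a glycaemia-outcome correlation of 0.7, a between-arm glycaemic gap of 0.5 or 0.8 SD, and 16 per arm. The total effect is 0.7 × gap, that is 0.35 or 0.56. If the glucose covariate measures the relevant glycaemia with reliability r, the adjusted arm difference is total × (1 − r).

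| Gap (SD) | Reliability | Total × (1 − r) | Simulated | Rejections at nominal 5% |
|---|---|---|---|---|
| 0.5 | 0.5 | 0.175 | 0.177 | 8.1% |
| 0.5 | 0.3 | 0.245 | 0.248 | 11.5% |
| 0.8 | 0.5 | 0.280 | 0.281 | 13.9% |
| 0.8 | 0.3 | 0.392 | 0.393 | 20.9% |

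So 50-70% of a fully glycaemic effect survives adjustment and looks independent. With a perfect measure the bias vanishes (rejections 5.0% and 5.4%), but the simulation has no other common cause of glycaemia and outcome, which randomisation does not guarantee.

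**The case against.** The plan is more careful than its hypothesis suggests. It does not say that HbA1c will fail to separate, only that it expects no drop large enough to confound. It volunteers the 12-week figure in order to argue that the change is small, adds the laboratory argument, commits to adjustment, and itself warns against a causal reading of glucose. The primary objective already asks the total-effect question, HbA1c is already a secondary outcome, and the trial calls itself a pilot. All of this stands, and it makes the point one of interpretation.

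Three stronger readings are tempting, and the documents do not support them.

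- A reader might infer that the cited study proves the duration premise false. It used another drug in a drug-naive population, so it weakens the premise only.
- A reader might infer that the toxicity of hyperglycaemia contradicts the in vitro argument. It does not address a change as small as 20 mg/dL. That argument is undocumented, not refuted.
- A reader might infer that the plan will test HbA1c, probably find no significance, and conclude a direct effect. Section 7 contains no such rule, and whether non-significance is likely depends on an SD that the documents do not give: power exceeds 50% in three of the eight cells in step 4.

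The objection does not remove the design limit. That limit follows from the missing comparator and the associative adjustment, whatever the 12-week figure shows.

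**Conclusion.** The concern holds as a limit on what may be concluded. The design supports a statement about adding canagliflozin versus placebo. It does not support one about benefit independent of HbA1c, and neither the duration rationale, the laboratory argument nor the glucose covariate supplies what is missing. The validity of the randomised CD34+ comparison is not in question.

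The structural conclusion needs no numerical assumption. The figures illustrate it: under the assumed SDs, the trial would detect an HbA1c gap of the cited size with power anywhere from 18% to 82%, so a non-significant difference could not be taken as equal glycaemia. The 50-70% carry-over after adjustment rests on the assumed reliabilities of 0.3-0.5 and on full mediation.

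**What to change.** - In section 6, Study Design Overview, delete the rationale that the trial is too short for a confounding HbA1c drop.
- In the synopsis and section 1, word the confirmatory hypothesis as the effect of adding canagliflozin versus placebo on CD34+ outcomes, in line with the primary objective in sections 2 and 6.
- In section 7, state that independence from glycaemia will not be concluded, and that any result adjusted for glucose or HbA1c is exploratory.
- Report the between-arm HbA1c difference at weeks 8 and 16 with its 95% CI beside the primary result, and note that a non-significant difference is not evidence of equal glycaemia.

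The cost is protocol and SAP wording plus one reported comparison. No new patients, visits or assays are needed: HbA1c is a listed secondary outcome, and section 6 schedules all secondary measures at weeks 0, 8 and 16. The section 6 biochemistry list does not name HbA1c, so it should be added there for consistency. The downside is a less ambitious stated claim.
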